1.4 Device/Treatment Groups

Only one device group is included in this study.

1.5 Sample Size

1.5.1 Sample size calculation for the primary efficacy analysis:

In order to achieve 90% power to detect a clinically significant difference of 10 dB in free-field hearing thresholds or 10 SNR between the unaided situation and the ATB System at the 3 months visit with Fisher's non-parametric permutation test for paired observations, one-sided test with significance level 0.025, on the ITT population 11 (PTA-4) and 13 (SNR) evaluable subjects are needed. The sample size was calculated using simulation on study id CBAS5675 (Cochlear 2017) data which used the simulated ATB system on Mixed/Conductive subjects. The within subject SD for change Unaided to ATB in PTA4 was 9.5 dB and 11.3 SNR. Since significant result want to be detected in both arms (SSD and Conductive/Mixed) 13+13=26 subjects should be included in the investigation.

1.5.2 Sample size estimation for the primary safety analysis at 6 months

Primary safety analysis will be evaluated at 6 months and an estimation of 50 subjects results in 25 patient years at 6 months which will yield enough safety data for the primary safety analysis. At the 12 months analysis 50 subjects results in 50 patient years.

1.5.3 Overall sample size considerations

In order to achieve 90% power both for the primary analysis (PTA4 and SNR, Investigational Device vs. unaided) and the primary safety analysis, 50 evaluable subjects are needed. Each arm SSD and Conductive/Mixed should at least consist of 13 patients to assure a power of 90% in both arms for the primary analyses.

2 STUDY POPULATIONS

2.1 Definition of Study Populations

The final definition of the analysis sets (ITT, PP and Safety) will be taken at the clean file meeting before database lock.

Protocol:

Clinical performance of a new implant system for bone conduction hearing

Protocol No:

CBAS5539

Version:

1.0

Page 10 of

22

2.1.1 *Intent-to-Treat Population (Full Analysis Set)*

The Intention-to-Treat population (ITT) will include all subjects who have undergone surgical intervention.

2.1.2 *Per-Protocol Population*

The Per Protocol population (PP) will include subjects that have completed the investigation according to the protocol. Subjects that were incorrectly included or were considered major protocol violators should be removed from the PP population.

2.1.3 *Safety Population*

The Safety population consists of all surgically treated subjects

3 STUDY VARIABLES

3.1 Baseline variables

3.1.1 *Demographics*

- Age (years), calculated from date of birth and date of
- Gender
- Ethnicity
- Nicotine use
- Site
- Country

3.1.2 *Baseline Characteristics*

- Treatment ear
 - Right
 - Left
- Type of hearing loss
 - Conductive/mixed
 - SSD
- Aetiology
 - (Chronic) Infection
 - Tumour
 - Trauma
 - Malformation
 - Otosclerosis
 - Other
- Current hearing aid
 - Yes
 - No

3.1.3 *Medical and Surgical History*

- Medical history will be coded using CTCAE.
- Surgical history will be coded using CTCAE.

Protocol:

Clinical performance of a new implant system for bone conduction hearing

Protocol No:

CBAS5539

Version:

1.0

Page 11 of

22

3.1.4 Prior and Concomitant Medications

Prior medication is defined as medication used up surgery. Concomitant medications are medications used from Surgery to end of study. Medications are coded according to WHO CC ATC.

3.1.5 Concomitant Treatments/Procedures

Concomitant Treatments/Procedures between Visit 1 and end of study will be collected. These terms will not be coded.

3.2 Efficacy Variables/endpoints

3.2.1 Primary Efficacy Variables/endpoints

- Threshold audiometry: PTA4 (mean of 500, 1000, 2000 and 4000Hz) at visit 1 (unaided) vs 3 months post-surgery (aided).
- Change in Adaptive speech recognition in noise (50% performance) from unaided versus Investigational device at the 3 months visit.

3.2.2 Secondary Efficacy Variables/endpoints

- Abbreviated Profile of Hearing Aid Benefit (APHAB) at visit 1 (unaided), m 3, m 6 and m 12:
 - Global score
 - Ease of Communication
 - Reverberation
 - Background Noise
 - Aversiveness
- Thresholds audiometry: PTA-4, 250, 500, 1000, 2000, 3000, 4000, and 6000 Hz at visit 1, w 4, m 3, m 6 and m 12
- Speech perception in quiet (50dB, 65dB and 80dB SPL) at visit 1, w 4, m 3, m 6 and m 12
- Adaptive speech recognition in noise (50% performance) at visit 1, w 4, m 3, m 6 and m 12
- Feedback measurement at each frequency at visit w 4, w 6, m 3, m 6 and m 12
- Generic quality of life scale: Health Utility Index (HUI) at visit 1 (unaided), m 3, m 6 and m 12:
 - Health related quality of life score for overall health
 - Vision score
 - Hearing score
 - Speech score
 - Ambulation/mobility score
 - Dexterity score
 - Self-care score
 - Emotion score
 - Cognition score
- The Speech, Spatial and Qualities of Hearing Scale (SSQ) at visit 1 (unaided), m 3, m 6 and m 12

Surgical variables

- Soft tissue thickness (mm)
- Surgery time (time of first incision to time of last suture), (min)

Protocol:

Clinical performance of a new implant system for bone conduction hearing

Protocol No:

CBAS5539

Version:

1.0

Page 12 of
22

- Type of anaesthesia
- Soft tissue thinning performed
 - Yes
 - No
- Bone polishing/removal below the actuator site performed
- BI300 length
 - 3 mm
 - 4 mm
- Location of BI300 Implant
- Surgical incision/location

Questions about usage will be collected at w 6, w 12, m 6 and m 12:

- Daily use of sound processor (hours/day)
- Softpad use
- Question about comfort with the SP, using VAS, will be collected at w 4, w 6, m 3, m 6 and m 12.
- Magnet choice will be recorded at w 4, w 6, w 12, m 6 and m 12.

BC Direct thresholds at visit 1, w 4, w 6, m 3, m 6 and m 12

3.3 Safety Variables/Endpoints

3.3.1 Implant site evaluation

Evaluation about numbness around the implant site will be performed at w 2, w4, w 6, m 3, m 6 and m 12.

- Total sensibility %
- Gnostic sensibility % (cotton swab) at 30 mm and 60 mm for Cranial, Caudal, Anterior and Posterior
- Vital sensibility % (sharp wooden) at 30 mm and 60 mm for Cranial, Caudal, Anterior and Posterior

3.3.2 Adverse Events

Adverse events from visit 2 and onward will be presented.

- Adverse Event (AE) is all reported events
- Adverse Device Effect (ADE) is events that is Related to the device (Probably) or Related to the procedure (Probably)
- Serious Adverse Event (SAE) is events that has been marked as Serious
- Serious Adverse Device Effect (SADE) is events that has been marked as Serious and also marked as Related to the device (Probably) or Related to the procedure (Probably)
- The following AEs are defined as adverse events of special interest (AESIs):
 - AE that interfere with the daily use of the medical device(s)
 - AE at the site of the implant that lead to
 - Revision surgery including explantation
 - Severe soft tissue complication
 - Prescription of antibiotics

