7.2 Adverse Event (AE) and Serious Adverse Event (SAE)

7.2.1 Definitions

| Term | Definition |
|--|---|
| Adverse Event (AE) | 
Any untoward medical occurrence, unintended disease or injury, or untoward clinical signs (including abnormal laboratory findings) in subjects, users or other persons, whether or not related to the medical device used in the investigation.
 
NOTE 1 This definition includes events related to the investigational medical device or the comparator.
 
NOTE 2 This definition includes events related to the procedures involved.
 |
| Adverse Event of Special Interest (AESI) | 
An AESI is an AE of scientific and medical concern specific to the sponsor's product(s).
 
The reporting requirements from the investigator to CBAS for an AESI will be the same as the reporting requirements for an SAE
 |
| Adverse Device Effect (ADE) | Adverse event related to the use of an investigational medical device |
| Serious Adverse Event (SAE) | 
Adverse event that
 
a) led to death
 
b) led to serious deterioration in the health of the subject, that either resulted in
 
 • a life-threatening illness or injury • a permanent impairment of a body structure or a body function • in-patient or prolonged hospitalization • medical or surgical intervention to prevent life-threatening illness or injury or permanent impairment to a body structure or a body function |

| | |
|---|---|
| | 
c) led to foetal distress, foetal death or a congenital abnormality or birth defect
 
Note - Planned hospitalization for a pre-existing condition, or a procedure required by the CIP, without serious deterioration in health, is not considered a serious adverse event.
 |
| Serious Adverse Device Effect (SADE) | Adverse device effect that has resulted in any of the consequences characteristic of a serious adverse event |
| Unanticipated Serious Adverse Device Effect USADE | Serious adverse device effect which by its nature, incidence, severity or outcome has not been identified in the current version of the risk analysis report |

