7.2.2 Handling and reporting of AEs and ADEs

Subjects will be carefully monitored during the investigation for possible adverse events and appropriate treatment of the subject will be initiated.

Any adverse events observed will be fully investigated by the investigator and documented in the case report form (CRF) including assessment of seriousness, severity (mild, moderate or severe) and relationship to the medical device.

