| a causal relationship between the SAE and the investigational medical device, a comparator device, diagnostic or therapeutic procedures performed as part of the clinical trial or other conditions of the trial conduct cannot be excluded | Germany | immediately | German SAE Report Form for single reports |
| | all other countries where the clinical trial is performed | immediately | MEDDEV 2.7.3 Summary Table |
| a causal relationship between the SAE and the investigational medical device, a comparator device, diagnostic or therapeutic procedures performed as part of the clinical trial or other conditions of the trial | Germany | quarterly | MEDDEV 2.7.3 Summary Table (sheet 2) |
| | all other countries where the clinical trial is performed | quarterly | MEDDEV 2.7.3 Summary Table (sheet 1) |

CBAS5539 CIP Version 5

| | | | |
|--------------------------------|--|--|--|
| conduct can be excluded | | | |
|--------------------------------|--|--|--|

Safety Reporting in The Netherlands

In the Netherlands serious adverse events will be reported by the sponsor (or its representative Factory CRO for Medical Devices) to the accredited Ethics Committee that approved the protocol and Competent Authorities.

Reporting Timelines to the Ethics Committee:

The Ethics committee requires that all SAEs occurring in all participating sites in the Netherlands and all foreign countries will be reported. The timelines and reporting requirements are as follows:

1. An SAE which indicates an imminent risk of death, serious injury, or serious illness and that requires prompt remedial action for other patients/subjects, users or other persons or a new finding to it: immediately, but not later than 7 calendar days after awareness by sponsor of a new reportable event or of new information in relation with an already reported event.
2. All other SAEs will be reported within 15 calendar days.

Reporting to the Ethics Committee will occur by completing the SAE form in the ToetsingOnline portal (<https://toetstingonline.ccmo.nl>). These SAEs are automatically forwarded to the Ethics Committee.

Reporting Timelines to the Competent Authority in the Netherlands:

IGZ requires that all SAEs (device-related and not device-related) occurring in all participating sites in all participating countries will be reported.

The reporting timelines are as follows:

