10.6.2 Adverse Events

Adverse Events and Serious Adverse Events will be presented overall and by relationship (Device related) both totally and per predefined Adverse Event, System Organ Class and Preferred Term.

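### SAP 3.3.2 counts procedure-only events as Adverse Device Effects, so the ADE and SADE tables can overstate device-related events as the protocol defines them

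*SAP*

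**What the plan says.** **Protocol.** Section 7.2.1 defines an ADE as "Adverse event related to the use of an investigational medical device". A SADE is built on it: "Adverse device effect that has resulted in any of the consequences characteristic of a serious adverse event". Procedure-related events appear in that table only as a note to the wider Adverse Event definition: "This definition includes events related to the procedures involved". Section 7.2.2 asks the investigator to document each event, "including assessment of seriousness, severity (mild, moderate or severe) and relationship to the medical device". Section 10.6.2 plans to present AEs and SAEs "overall and by relationship (Device related"), both in total and by term.

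**SAP.** Section 3.3.2 says "Adverse Device Effect (ADE) is events that is Related to the device (Probably) or Related to the procedure (Probably"). A SADE is an event "marked as Serious and also marked as Related to the device (Probably) or Related to the procedure (Probably"). Section 4.11.2 gives an overview with rows for AE, SAE, ADE, SADE and AESI, and summaries of the same five categories by CTCAE term. The table list in section 7.1 has ADE and SADE tables but none restricted to device-related events. Section 6 states that the analyses are unchanged from the protocol.

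**The concern.** The two documents use one label for two quantities. The protocol's ADE answers how many events were related to the device. The SAP's ADE answers how many were marked as related to the device or to the operation that placed it.

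Every subject in the Safety population has had surgery (SAP 2.1.3), and protocol 7.4 foresees surgical complications, so events related only to the procedure are a realistic possibility. If they enter the ADE and SADE rows, a reader of the 6-month primary safety analysis will take them for device effects. No other planned table would allow them to be separated out. The presentation promised in protocol 10.6.2 would be missing, with no declared departure to alert the reader.

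**Working it through.** The documents state no ADE count, rate or threshold, so there is no planned figure to reproduce. The check sets the definitions side by side and then counts.

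**Step 1: the definitions.**

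| Item | Protocol | SAP |
|---|---|---|
| ADE | Related to use of the device (7.2.1) | Device (*Probably*) or procedure (*Probably*) (3.3.2) |
| SADE | Serious ADE, hence device-only (7.2.1) | Serious, plus the same either/or rule (3.3.2) |
| Procedure-related events | Note under AE, not under ADE (7.2.1) | Inside ADE and SADE (3.3.2) |
| Output by relationship | Device related (10.6.2) | Combined ADE and SADE only (4.11.2, 7.1) |
| Declared change | – | None (6) |

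The protocol treats device and procedure relatedness as distinct elsewhere too: section 7.3, on safety reporting in Germany, names them as two things that may apply separately or together.

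**Step 2: the effect on the count.** Let

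- D = events marked *Probably* related to the device;
- P = events marked *Probably* related to the procedure and not related to the device.

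The SAP count is D + P. Take *Probably* as the affirmative mark in the eCRF (an assumption, since neither document shows the scale). The protocol count is then D, and

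SAP count − protocol count = (D + P) − D = P ≥ 0.

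The ADE count is too high by P whenever P is above zero. The same holds for SADE, using only the serious events in P.

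**Step 3: scale.** The planned number is 50 subjects (protocol 10.3.3, SAP 1.5.2). One subject is 1/50 = 2 percentage points. A subject moves the subject-level percentage only if he or she has no other qualifying ADE. In the event-level count each event in P adds one. Neither document gives event figures from which P could be estimated.

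**Step 4: what is not touched.** All-AE and SAE counts do not use relatedness. The AESI list in SAP 3.3.2 is defined by consequences and site, not by the ADE rule. The interim go/no-go (protocol 10.9, SAP 5) focuses on SAEs and AESIs.

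**The case against.** **Surgical risk sits under the device heading.** Protocol 9.2, on anticipated adverse device effects, opens with the risks of surgery and anaesthesia, and the procedure note under AE does not expressly exclude such events from ADE. This shows loose usage in a risk narrative. It does not displace the explicit definition in 7.2.1.

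**Little depends on the count.** Adverse events are analysed descriptively only (SAP 4.1), and no hypothesis or decision rule uses ADE or SADE. This stands and limits the consequence: the matter is the correct labelling of a safety output, not a changed conclusion.

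**The rule is open and the split may be recoverable.** SAP 3.3.2 states the combination plainly and names the two relationships separately, which suggests that both are recorded. Listings are decided outside the SAP (7.3), so their content is unknown. This supports the view that a device-only row is cheap to produce. It does not put that row in the planned tables.

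**A stronger reading that does not hold.** A reader might infer that *Probably* is one grade among several, so that device-related events at other grades are dropped and the ADE count is also too low. The documents do not support this. Neither shows the eCRF scale, protocol 7.2.2 grades severity but gives no grades for relationship, and the ADE definition sets no degree of certainty. *Probably* may be the only affirmative option. The protocol wording that a causal link with the device, with trial procedures or with "other conditions of the trial conduct cannot be excluded" is no benchmark either. It is the trigger for immediate SAE reporting to one national authority (7.3), and it pools device and procedure itself.

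**Conclusion.** SAP 3.3.2 departs from protocol 7.2.1 by admitting events related only to the procedure into ADE and SADE. The departure is undeclared, and it leaves the device-related presentation of protocol 10.6.2 without a planned table. As written, the plan can overstate device-related events by P, the number of *Probably* procedure-only events. The documents do not allow P to be sized. The bound per subject is 2 percentage points at 50 subjects.

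The direction of the error rests on *Probably* being the affirmative option. If the eCRF holds other affirmative grades, the net difference cannot be signed from the documents. Nor should it be inferred that every surgical complication is miscounted: only those marked *Probably* related to the procedure and not related to the device are.

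**What to change.** 1. In SAP 3.3.2, define ADE and SADE by relationship to the device, as in protocol 7.2.1.
2. Add a separate row for procedure-related events to the overview table and the CTCAE-term tables (SAP 4.11.2 and 7.1).
3. If a combined device-or-procedure category is also wanted, label it as combined and declare it in SAP section 6.
4. State the eCRF causality categories and which of them count as related. The protocol prescribes no cut-off, so the SAP should make its choice explicit.

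The cost is SAP wording and one or two table rows. If the eCRF holds device and procedure relationship as separate items, as the SAP wording suggests, no new data are needed.

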3.3.3 Device deficiency

Device deficiency will be collected at d 0, w 2, w 4, w 6, m 3, m 6 and m 12.

- Has any device deficiency occurred?
 - Yes

STATISTISKA KONSULTGRUPPEN		Statistical Analysis Plan	
Protocol: Clinical performance of a new implant system for bone conduction hearing		Protocol No: CBAS5539	
		Version: 1.0	Page 13 of 22

- No

3.3.4 Audiogram

Audiogram at Visit 1, Air condition/Bone conduction, Right/Left (transferred to test side/Non test side), Unmasked/Masked for 250, 500, 750, 1000, 1500, 2000, 3000, 4000, 6000 and 8000 Hz. At 3 months visit and 12 months visit test side audiogram, bone conduction (unmasked and if needed masked) thresholds at 250, 500, 750, 1000, 1500, 2000, 3000, 4000 and 6000Hz will be collected.

4 STATISTICAL METHODOLOGY

4.1 General Methodology

Since all included subjects will have measurements of the primary and important secondary efficacy variables for unaided hearing, with the Investigational device and with a Baha power sound processor on a Baha Softband, all statistical analyses will be paired. All statistical analyses will be non-parametric. In order to choose the most powerful test, the Fisher's non-parametric permutation test for paired observations will be used for all paired analyses of continuous variables. The permutation tests use the measured values and not only the ranks in the calculations. For paired analysis of dichotomous and ordered categorical variables the Sign test will be used.

The analyses will be performed in the following priority:

1. Investigational Device vs. Unaided
2. Investigational Device vs. Baha power sound processor on a Baha Softband

In addition to the change variables the distribution of all efficacy variables will be presented by visit, where applicable.

The main efficacy analysis will be performed on the ITT population and complementary efficacy analyses will be performed on the PP population. The main analysis will be performed after the 3 month visit. A complementary analysis will be performed 9 months after the main analysis (12-month visit). All significance tests will be one-sided and performed at the 2.5% significance level to demonstrate an improvement with Investigational Device.

The hierarchical testing procedure below is introduced to guarantee that the probability of Type I error is < 2.5% for all confirmative statements. The order of the hierarchical testing procedure will be:

1. PTA 4 pre-operative unaided vs 3 months (Primary efficacy analysis)
2. Adaptive speech recognition in noise (50% performance), speech to noise ratio (SNR) pre-operative unaided vs 3 months
3. Speech in quiet at 65dB SPL pre-operative unaided vs 3 months
4. APHAB Global pre-operative unaided vs 3 months aided
5. Hearing attribute (HUI-III) pre-operative unaided vs 3 months
6. Mean of the 12 items in the SSQ pre-op unaided vs 3 months

If the first analysis is significant the probability mass 0.025 will go to the second analysis. If the second analysis is also significant the probability mass 0.025 will go to the third analysis and so on. When the first non-significant analysis is reached this and all analyses thereafter will be non-confirmative while the previous analyses will be confirmative. If the first analysis is non-significant no analysis will be confirmative.

STATISTISKA KONSULTGRUPPEN		Statistical Analysis Plan	
Protocol: Clinical performance of a new implant system for bone conduction hearing		Protocol No: CBAS5539	
		Version: 1.0	Page 14 of 22

The hierarchical testing will be made for each arm separately (SSD and Mixed/Conductive) and not totally.

We plan to analyse the similarity of the primary efficacy results among sites using non-parametric one way analyses of variance (Kruskal-Wallis test) of the difference between Unaided and ATB at 3 months. This will only be made totally and not by SSD and Mixed conductive.

Imputation of missing values will be performed for all efficacy variables. No imputation of baseline values or baseline carry forward will be made. Imputations will be made according to the following rules:

1. If a value is missing at the end of a patient, last observation will be carried forward.
2. If a missing value is occurring between two time points with values, an interpolation will be made for continuous variables and for categorical variables the value from the previous visit will be carried forward.

The distribution of continuous variables as well as change in continuous variables will be given as n, mean, SD, SEM, Median, Min and Max and the distribution of dichotomous and categorical variables will be given as number and percentages. One sided 97.5% CI will be presented where applicable.

Numbness, Adverse Events, Device deficiencies, Comfort, Usage, Surgical variables, Demographics, Baseline, Questions, Magnet strength variables will only be analysed descriptively.

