1.2 Aim

The aim of the investigation is to demonstrate that the ATB System provides an improvement in hearing outcomes and quality of life compared to unaided hearing in patients with a conductive or mixed hearing loss or single-sided sensorineural deafness (SSD).

The aim is also to measure and present preoperative audiological test results with a Baha BP110 Power Sound Processor on a Baha Softband in relation to the Investigational device. Safety parameters will be collected.

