6.7 Health Utility Index (HUI23)

The Health Utilities Index (HUI®) 23S15Q is a generic preference-based system for measuring comprehensive health status and health-related quality of life (HRQL). HUI provides descriptive evidence on multiple dimensions of health status, a score for each dimension of health, and a HRQL score for overall health. Health dimensions include vision, hearing, speech, ambulation/mobility, pain, dexterity, self-care, emotion and cognition. Each dimension has 3-6 levels. The version in this clinical investigation uses a recall time of 1 week.

The subjects will complete the HUI at Visit 1, 6 and 8.

- At Visit 1, the subjects shall complete the HUI questionnaire prior to the Softband test and with respect to their current hearing situation
- At Visit 6 and 8, the subjects shall complete the questionnaire for the aided situation (with the Investigational device).

The license to use the HUI questionnaire is purchased from Health Utilities Inc., [name].

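### The protocol aims to demonstrate better quality of life, but this is in no formal objective and the overall HUI score, tested only outside the SAP hierarchy, can never be confirmative

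*SAP*

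**What the plan says.** Protocol 1.2, like the synopsis, states the aim as "to demonstrate that the ATB System provides an improvement in hearing outcomes and quality of life compared to unaided hearing".

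Protocol 6.7 describes HUI as yielding "a score for each dimension of health, and a HRQL score for overall health", so a dimension score and the overall score are separate outputs. SAP 3.2.2 labels HUI a generic quality of life scale, the only instrument so labelled, and lists first among its scores "Health related quality of life score for overall health".

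SAP 4.1 sets a fixed-sequence hierarchy, run separately in the SSD and the Conductive/Mixed arm, to "guarantee that the probability of Type I error is < 2.5% for all confirmative statements". The steps, all at 3 months, are PTA4, speech in noise (SNR), speech in quiet at 65 dB, APHAB Global, the HUI-III hearing attribute and the SSQ-12 mean. Step 5 reads "Hearing attribute (HUI-III) pre-operative unaided vs 3 months".

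Outside the hierarchy, SAP 4.10.2 lists HUI-III for Fisher's paired permutation test at 3, 6 and 12 months, in total and by arm. Read with SAP 3.2.2, this covers the overall score.

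**The concern.** To demonstrate something is confirmatory language, and under SAP 4.1 only a result inside the hierarchy can be confirmative. If all six steps succeed in both arms, the trial still has no error-controlled result on the overall quality-of-life score, the measure that matches the second half of its aim most directly. That score is tested at a nominal 2.5%, with no adjustment, alongside many other secondary tests.

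Step 5 also carries the HUI name, so a reader of the results could take a significant hearing attribute for a general quality-of-life finding. SAP section 6 records no departures from the protocol, so the SAP does not acknowledge the gap.

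**Working it through.** **1. Aim, objectives and tests side by side.**

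| Level | Hearing outcomes | Quality of life |
|---|---|---|
| Aim (Protocol 1.2, synopsis) | Named | Named |
| Formal objectives (Protocol 4.3, 10.1; SAP 1.1) | Named, measured and self-reported | Not named; HUI is placed under self-reported hearing outcome |
| Hierarchy (SAP 4.1) | Six steps, including the HUI hearing attribute | Overall HUI score in 0 of 6 steps |
| Other secondary tests (SAP 4.10.2) | Yes | Overall score, non-confirmative |

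The gap therefore opens between the aim and the objectives, and the hierarchy inherits it. Protocol 6.5 describes APHAB as benefit from amplification, and 6.6 describes SSQ as self-reported auditory disability. Neither is presented there as a quality-of-life scale.

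**2. The plan's error rate.** Inputs: "All significance tests will be one-sided and performed at the 2.5% significance level", and the passing rule "If the second analysis is also significant the probability mass 0.025 will go to the third analysis and so on". Within an arm, take the first step in the sequence whose null hypothesis is true. A false confirmative statement requires that step to be rejected, and it is tested at 0.025. The chance of any false confirmative statement is therefore at most 0.025, which reproduces the SAP's figure.

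**3. The same with seven steps.** The argument does not use the number of steps, so the limit stays at 0.025 per arm. Steps 1 to 6 are decided before step 7 is reached, so none of their results can change. Across both arms, if they are independent, the chance of at least one false confirmative claim is at most 1 − (1 − 0.025)² = 0.0494, with six steps or with seven.

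**4. What step 7 could detect.** The documents give no HUI effect size or SD, so only a standardised change d (mean change divided by the SD of change) can be shown. The smallest arm is 13 (SAP 1.5.3). A rough normal formula gives d = (1.960 + 1.282)/√13 = 3.242/3.606 = 0.90. The paired t version, solving for power in the noncentral t with n − 1 degrees of freedom and noncentrality d√n, gives:

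| n in arm | d at 90% power | d at 80% power |
|---|---|---|
| 13 (stated minimum) | 0.98 | 0.85 |
| 25 (assumed, 50/2) | 0.68 | 0.58 |
| 37 (assumed, 50 − 13) | 0.55 | 0.47 |

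These figures are for the test taken alone.

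**5. Reaching step 7.** As an illustration, assume every step has the same power and the steps are independent. The chance of passing the first six is 0.95⁶ = 0.735, 0.90⁶ = 0.531 or 0.80⁶ = 0.262. The chance of confirming step 7 as well is 0.698, 0.478 or 0.210. Positive correlation between outcomes would raise these figures.

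**6. Baseline condition.** Protocol 6.7 has HUI answered at Visit 1 for the current hearing situation, and Protocol 10.5.2 repeats that comparison. APHAB and SSQ must be answered unaided even by device users (Protocol 6.5, 6.6). The hypothesis in SAP 4.10.2 uses the preoperative hearing situation for the HUI hearing attribute, yet step 5 in SAP 4.1 and the HUI entry in SAP 3.2.2 say unaided. For a subject with a current aid, any HUI change is measured from that aided state.

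**The case against.** The hierarchy follows the formal objectives. Quality of life is in none of them, and for an objective on self-reported hearing outcome the hearing attribute is a natural HUI component to test. A narrative aim need not turn each of its elements into a confirmatory endpoint. This stands, and it means the SAP does not contradict a formal objective.

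A reader might infer that no step touches quality of life at all. The documents do not support that. Step 5 is one dimension of a health-related quality-of-life instrument, and an exclusion criterion speaks loosely of quality-of-life scales in the plural. The separation of dimension and overall scores in Protocol 6.7 favours the narrower statement: the overall score is absent from the hierarchy.

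A reader might also infer that overall quality of life is neglected. It is not. It is prespecified, tested and tabulated, pooled and by arm. Only confirmative status is missing.

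Nor would a seventh step fully deliver the aim. The aim's comparator is unaided hearing, and the HUI baseline is not unaided for everyone. Power at the smallest arm is also modest. Both points limit what the step can show, but neither is a reason to omit a last step that uses no alpha. Finally, no document plans a quality-of-life claim from step 5, so the risk of misreading is a possibility only.

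**Conclusion.** The mismatch is real but limited. The aim promises to demonstrate a quality-of-life improvement, no formal objective carries it, and the overall HUI score can never be confirmative. The primary analysis and the six existing steps are unaffected. A seventh step would move the number of confirmative tests of overall quality of life from none to one per arm, with the per-arm error still at most 0.025.

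A success there would show improvement over the preoperative, current hearing situation. It would show improvement over unaided hearing only for subjects without a current aid. The detectable change of 0.98 SD at 13 per arm rests on a paired t approximation to the permutation test and on an unknown HUI SD. The conclusion about the hierarchy rests on neither.

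**What to change.** - In SAP 4.1, append step 7: overall HUI-III health-related quality-of-life score at 3 months against the preoperative (current) hearing situation, Fisher's paired permutation test, one-sided 0.025, per arm.
- In SAP 4.10.2, add the matching hypothesis, in the same form and direction as the one for the hearing attribute.
- Replace unaided in step 5, and in the HUI entry of SAP 3.2.2, with the baseline condition used in Protocol 6.7 and SAP 4.10.2.
- State in the SAP that for subjects with a current aid HUI does not measure change from unaided, and that step 7 has limited power at the minimum arm size and depends on all six earlier steps.

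Cost: a few lines in a revised SAP, best settled before the 3-month lock. HUI is already collected at Visits 1, 6 and 8, and no alpha is taken from steps 1 to 6.

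If the step is not added, report quality of life as non-confirmative and do not claim it as demonstrated. Rewording the aim itself would be a protocol amendment, with the signatures and approvals in Protocol 11.3 and 12.6.1, so it costs more than the SAP change.
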